Active training: In between the presentation of the cue and target, three "distractor" boxes appear at irrelevant locations at random times. Subjects are instructed to ignore these boxes. It is the active ignoring of these boxes, while maintaining attention voluntarily at the cued location that is proposed to reduce subjects' stimulus-driven attention and reduce excessive VAN activity. **Sham training:** Subjects perform the same

number of trials, of the same task, with the exception that the "distractor" boxes never appear. Thus, subjects still have to voluntarily direct attention, but they do not get practice ignoring irrelevant distractors. Both subjects and clinical interviewers will be

blinded to active versus sham treatment. Subjects will be randomized to treatment arm.

3.b Treatment Regimen

Half of the subjects will be randomized to active cognitive training and half will be randomized to sham training. Children will participate in 8 total 30-minute training sessions, twice a week for 4 weeks.

3.c Method for Assigning Subjects to Treatment Groups

Subjects will be randomized to active vs. sham treatment on a 50/50 basis.

3.d Subject Compliance Monitoring

Subjects will be participating in the cognitive training program twice a week for four weeks in the presence of a trained research assistant.

3.e Blinding of Study Drug

Subjects will not be aware if they are participating in the active or sham treatment.

F Study Procedures

F1 Screening for Eligibility

Subjects will be screened over the phone standardized parent-report psychiatric instruments (Screen for Anxiety and Related Disorders, SCARED; and Mood and Feelings Questionnaire, MFQ).

F2 Visit 1

Child/Parent In-Office Assessment:

Parents will begin by completing Kiddie Schedule for Affective Disorders and Schizophrenia Present and Lifetime Edition (K-SADS-PL), the Pediatric Rating Scale, (PARS), and the Family Interview for Genetic Studies (FIGS) with trained research staff. These semi-structured interviews will be audio taped and will only be listened to by study staff. Parents will also complete additional questionnaires. The child will participate in a computer game that is designed to test various aspects of their attention.

The child will rest their chin on a chin rest and their eye movements will be recorded. There are three different versions of the game. In each version, the computer game involves looking at a central "+" sign and pressing a button when a target appears in

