The child will participate in 8 thirty minute training sessions, twice a week for four weeks. They will complete the cognitive training program that has been designed by [name].

On the day of sessions 2, 4, 6, and 8 subjects and parents complete the SCARED either in office or by a secure e-mail survey invitation via REDcap in order to assess anxiety over treatment. After session 8, subjects will be asked to rate tolerability of the training on a 5 point Likert scale.

F5 Visit 11

This visit will be after all 8 training sessions are completed and is identical to visit 1.

F6 Visit 12

This visit will be after all 8 training sessions and visit 11 are completed and is identical to visit 2.

Follow-up via Phone/Zoom

A member of the research team will explain that this is completely optional and will review the online survey process with the family over the phone or zoom. If the family agrees to participate, the research team member will e-mail a RedCap survey link that will start with the consent form. Researcher will walk participant through how to complete the surveys over the phone or zoom. Participants will have adequate time to review the consent document and there will be an e-mail address provided if the participant should have any questions. The participants e-signature through REdCap will have a time stamp. After the consent is signed, research staff will send an electronic copy of the signed consent document to the participant via e-mail.

G Statistical Plan

G1 Sample Size Determination and Power

Power analyses for two-tailed, two independent groups (active versus sham) comparisons were performed using G*Power 3.1. Based on prior work, we expect training to have a minimum effect size of 0.3 for changing symptoms of anxiety. Based on this effect size, we have 83% power to detect group differences in treatment effects (n=90, plus 10% failure). Power calculations are not computed for fMRI analyses because we have no effect size estimate; sample size is similar to other recent pilot studies.

G2 Interim Monitoring and Early Stopping

Subjects may withdraw from the study at any time. Each cognitive training session takes place in the lab. Study staff will converse with study subjects before and after each training session in order to assess for any adverse events.

G3 Analysis Plan / Statistical Methods

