The primary outcome will be reduction in symptoms of anxiety as measured by the SCARED in study Phase 2. Total SCARED scores at sessions 2, 4, 6, and 8 will be subtracted from the baseline SCARED score, yielding a delta SCARED score for each

visit. These data will be analyzed with a mixed random effects repeated-measures model. In this model, time, treatment (active versus sham), and time x treatment interaction are fixed effects; baseline SCARED scores and subject within treatment are random effects; and delta SCARED scores are the dependent variable. Our hypothesis predicts a significant time x treatment interaction, with a greater decrease in anxiety from pre- to post- training in the active relative to the sham group. Secondary outcomes will include symptoms of anxiety on the PARS and diagnostic status.

We will test whether active versus sham training significantly reduces symptoms in children with anxiety disorders. The primary outcome will be reduction in symptoms of anxiety as measured by the PARS. We will perform a 2 x 2 ANOVA with treatment arm (active versus sham) and time (pre- versus post-training) as effects of interest.

G4 Missing Outcome Data

We will use an intention-to-treat analysis and carry the last observation forward. Because this is a pilot study, we will also compare active versus sham treatment among completers in a follow-up analysis.

G5 Unblinding Procedures

The principal investigator will be made aware of each subject's assignment after that subject has completed all study procedures including post-treatment psychiatric assessment.

H Data Handling and Record Keeping

H1 Confidentiality and Security

Telephone conversations about the study, the consent process, and all portions of the study will take place in a private office. All subjects will be marked with a random identification number so names will not be recorded on any of the data. All data will be stored in locked filing cabinets and on password protected computers. Also, only the research team will have access to study information. Participants can refuse to answer any questions and withdraw from the study at any time.

H2 Training

All current study staff have extensive experience in study procedures, based on similar prior studies performed in the lab. Any new personnel will be trained by current study staff.

H3 Case Report Forms and Source Documents

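### The random effects listed for the SCARED model in G3 are all constant within a child, so unless another covariance structure is named the model assumes equal correlation between sessions, and the time x treatment test can be anti-conservative

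*Combined protocol and SAP*

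**What the plan says.** Section F4 sets the measurement times: "On the day of sessions 2, 4, 6, and 8 subjects and parents complete the SCARED". Section 3.b (Treatment Regimen) gives two training sessions a week for four weeks, so consecutive SCARED scores are about one week apart.

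G3 turns these into four change scores per child: "Total SCARED scores at sessions 2, 4, 6, and 8 will be subtracted from the baseline SCARED score". It then names the model: "These data will be analyzed with a mixed random effects repeated-measures model". The fixed and random parts are given together: "time, treatment (active versus sham), and time x treatment interaction are fixed effects; baseline SCARED scores and subject within treatment are random effects". The test that carries the hypothesis is also named: "Our hypothesis predicts a significant time x treatment interaction".

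G3 does not say whether time is a four-level factor or a linear trend. It gives no random slope, residual covariance structure, degrees-of-freedom method, sphericity correction or robust standard error. No significance level and no between-session correlation appear anywhere in the document.

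The second paragraph of G3, like section C1, names the PARS as the primary outcome and analyses it with a 2 x 2 ANOVA at two time points.

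**The concern.** A random effect that is constant within a child adds the same variance to all four of that child's scores and the same covariance to every pair of them. Baseline SCARED and subject are both of this kind. With independent residuals, the listed model therefore has compound symmetry: one correlation for all six pairs of sessions.

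That is doubtful for weekly symptom scores during a month of treatment. Scores one week apart are usually closer than scores three weeks apart. The sample also covers ages 7 to 17, three anxiety diagnoses and children with or without an SSRI, so different rates of change are plausible. In either case the contrast between early and late sessions varies more than the pooled within-child variance suggests. The standard error of time x treatment is then too small, and the error is towards false claims of benefit.

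If the structure and the coding of time are instead chosen at analysis, G5 matters. The principal investigator learns each child's assignment as that child finishes, so the choice could be made with allocation known.

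**Working it through.** **The plan's own figures.** There is no type I error or correlation to reproduce. The only operating figure is the 83% power in G1, which does not bear on this point.

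**Inputs.** From the documents: 90 children randomised 1:1 (45 per arm), four scores per child about a week apart, two-tailed testing. Assumed: a 5% level, all correlations, slope variances, measurement error and dropout.

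**Linear time, by formula.** The slope contrast is c = (-3, -1, 1, 3)/√20. Its true variance is c'Rc, where R is the true correlation matrix. The random-intercept model uses the pooled within-child variance instead, which is 1 minus the mean off-diagonal correlation. Under AR(1) with parameter ρ:

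- c'Rc = 1 + 0.1(5ρ - 6ρ² - 9ρ³)
- pooled variance = 1 - (3ρ + 2ρ² + ρ³)/6
- rejection rate ≈ 2[1 - Φ(1.96/√ratio)], where ratio = c'Rc / pooled variance

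For ρ = 0.8:

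- c'Rc = 1 + 0.1(4 - 3.84 - 4.608) = 0.5552
- pooled variance = 1 - (2.4 + 1.28 + 0.512)/6 = 0.3013
- ratio = 1.84, so the standard error is too small by a factor of 1.357
- rejection rate = 2[1 - Φ(1.96/1.357)] = 14.9%

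Any component that is stable within a child, including the baseline shared by all four deltas, cancels from the contrast and does not reduce the inflation.

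**Simulation under the null.** 40,000 trials per scenario. In balanced data the random-intercept model is the split-plot test: F on 3 and 264 df with time categorical, t on 268 df with time linear.

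| AR(1) ρ | Ratio | Linear, formula | Linear, simulated | Categorical, simulated |
|---|---|---|---|---|
| 0.3 | 1.31 | 8.7% | 8.8% | 5.4% |
| 0.5 | 1.53 | 11.3% | 11.5% | 5.7% |
| 0.7 | 1.74 | 13.7% | 13.8% | 6.3% |
| 0.8 | 1.84 | 14.9% | 14.8% | 6.6% |
| 0.9 | 1.94 | 16.0% | 16.2% | 6.8% |

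When compound symmetry is true, the test holds its level: 5.1% categorical, 5.0% linear.

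**Measurement error added to AR(1) 0.8, linear time.**

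- Independent error at 25% of variance: (0.75 × 0.5552 + 0.25)/(0.75 × 0.3013 + 0.25) = 0.6664/0.4760 = 1.40, giving about 10%.
- At 50%: 0.7776/0.6507 = 1.195, giving about 7%.

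**Children differing in slope.** With slope variance 0.05 to 5 per week squared and residual variance 1, type I error runs from 5.1% to 10.2% (categorical) and from 6.9% to 24.1% (linear).

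**Worst-case bounds.**

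- Categorical: the 5% critical value of F(3, 264) is 2.639, and P(F(1, 88) > 2.639) = 10.8%.
- Linear: 1.969/√3 = 1.137, and 2P(t on 88 df > 1.137) = 25.9%.

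**Is the covariance assumption the cause?** On the same simulated data, a Greenhouse-Geisser correction gives 4.7% to 5.1%, and a t test comparing per-child slopes between arms gives 4.9% to 5.2%, in every scenario. Carrying the last observation forward with 10% to 20% dropout moves the AR(1) figures by less than 0.3 points.

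**The case against.** The strongest reply is that G3 under-specifies the model rather than mis-specifies it. A repeated-measures mixed model may carry AR(1) or unstructured residuals beside the listed random effects, and the text rules out neither. Equal correlation is thus an inference, and if it happens to be true the test is sound. This stands, and it is why the point is worded conditionally. It does not remove the point: the plan writes out a concrete model, and fitting that model as listed with independent residuals can give too small a standard error.

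A reader might infer that the test runs at about 15%. The documents do not support that figure. It needs linear time, strong serial correlation, independent residuals and no measurement error all together, and none of these is stated. It is not a ceiling either. The wording leans towards time as a factor: deltas are formed separately for each visit, subject is nested in treatment as in a split-plot analysis, the next paragraph uses time as an ANOVA factor, and no slope is mentioned. On that reading the inflation under serial correlation is small.

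A reader might also infer that the trial's primary test is invalid. That goes too far. G3 gives two competing primary analyses, and the PARS ANOVA has two time points and a 1-df interaction, where the problem cannot arise.

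**Conclusion.** The point holds in conditional form. Unless another structure is specified, the SCARED model in G3 assumes equal correlation across sessions 2, 4, 6 and 8, and its time x treatment test is anti-conservative if that is false. The size depends mostly on how time is coded:

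- **Categorical time:** about 5-7% under assumed AR(1) of 0.3 to 0.9, and never above about 11%.
- **Linear time:** about 9-16% over the same range, about 7-10% if measurement error is added to AR(1) 0.8, and higher with large slope variation.

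The direction follows from the model; the size rests on assumed correlations. On the likelier categorical reading this is a modest defect, but it sits on the test the SCARED hypothesis relies on and costs little to remove. The change should be made. How much it matters to the trial's conclusion depends on whether SCARED or PARS is primary, which the plan must reconcile separately.

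**What to change.** In G3, replace the sentence on fixed and random effects so that it specifies:

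- session (2, 4, 6, 8) as a categorical fixed factor, with treatment and session x treatment;
- baseline SCARED as a fixed covariate rather than a random effect;
- an unstructured within-child covariance, fitted by REML with Kenward-Roger degrees of freedom;
- a standard error clustered on child as the named fallback if the model does not converge;
- if a linear trend in time is kept, a random slope for time per child.

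Other routes, such as a Greenhouse-Geisser correction or a comparison of per-child slopes, also restored about 5% in the check. What matters is that one valid method and the coding of time are fixed before allocation is known.

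The cost is SAP wording. Four visits need 4 × 5/2 = 10 covariance parameters, which 90 children can support. The downside is a slightly wider confidence interval and a small risk of non-convergence, which the fallback covers.

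### G3 enters baseline SCARED as a random effect with no fixed slope, so how far the arm difference in SCARED change is baseline-adjusted depends on an unstated coding

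*Combined protocol and SAP*

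**What the plan says.** The first paragraph of G3 (Analysis Plan / Statistical Methods) defines the outcome: "Total SCARED scores at sessions 2, 4, 6, and 8 will be subtracted from the baseline SCARED score". A positive delta is therefore improvement, and the same baseline value sits inside all four deltas of a child.

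The model follows: "In this model, time, treatment (active versus sham), and time x treatment interaction are fixed effects". The next clause places baseline among the random terms: "baseline SCARED scores and subject within treatment are random effects; and delta SCARED scores are the dependent variable". No fixed baseline term for SCARED appears anywhere, and nothing says how a continuous score with one value per child is to be coded as a random effect.

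On the test, G3 says "Our hypothesis predicts a significant time x treatment interaction", and the same sentence glosses this as a larger pre-to-post fall in anxiety in the active arm.

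Three other places matter. E1 puts the baseline assessment ahead of the random assignment to training. Section 3.c gives 1:1 allocation. C1 and the second paragraph of G3 name PARS as the primary outcome, whereas the first paragraph of G3 gives that status to SCARED.

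**The concern.** Baseline SCARED is a measured covariate, not a sampled grouping level. Because delta is baseline minus a later score, delta correlates with baseline by construction whenever the two scores are less than perfectly correlated (equal SDs). A fixed slope removes that part of the variation. A random effect may or may not do so, because three codings fit the G3 sentence:

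- **Per-child random slope on baseline.** Each child has one baseline value, so the term only reshapes the between-child variance.
- **Random intercept for each distinct baseline value.** Children who share a score are linked, which recovers part of the adjustment.
- **One overall random coefficient.** This behaves almost like a fixed slope, but its variance is estimated from a single draw, and it is an unusual choice.

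At stake are the precision of the arm difference in delta and the fact that analysts following the same sentence could report different estimates.

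**Working it through.** **Inputs.** From the documents: 90 children, 1:1, so 45 per arm; delta = baseline minus session score at sessions 2, 4, 6 and 8; last observation carried forward (G4), so the four deltas per child are largely balanced. Assumed, because the documents give none of them: equal SDs, baseline-to-session correlation rho of 0.5 to 0.8, SCARED mean 38 and SD 12, between-session correlation 0.5 to 0.8, two-sided alpha 0.05.

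**The plan's own figure.** G1 states "we expect training to have a minimum effect size of 0.3 for changing symptoms of anxiety" and "we have 83% power to detect group differences in treatment effects (n=90, plus 10% failure". Read as a standardised mean difference of 0.3 with 45 per arm, two-sided power is 29%, so 83% is not reproduced. Read as f = 0.3, power is 80.4% at N = 90 and 84.0% at N = 99. Read as a correlation of 0.3 at N = 90, it is 82.3% to 83.9%. The baseline term does not enter G1, so nothing below rests on this figure.

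**Step 1: a single visit, in SD² units.**
- Change score: Var = 2(1 − rho).
- Fixed baseline covariate: Var = 1 − rho².
- Ratio: 2(1 − rho)/(1 − rho²) = 2/(1 + rho).
- Equivalent children lost: 90 × [1 − (1 + rho)/2].

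| rho | change | adjusted | ratio | children lost of 90 |
|---|---|---|---|---|
| 0.5 | 1.00 | 0.75 | 1.33 | 22.5 |
| 0.6 | 0.80 | 0.64 | 1.25 | 18 |
| 0.7 | 0.60 | 0.51 | 1.18 | 13.5 |
| 0.8 | 0.40 | 0.36 | 1.11 | 9 |

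For scale, a contrast with 83% power on change scores would have about 92%, 90%, 88.5% and 87% with the fixed covariate.

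**Step 2: the extra variance is the imbalance carry-over.** 2(1 − rho) − (1 − rho²) = (1 − rho)². At rho 0.6: 0.80 − 0.64 = 0.16 = 0.4². An unadjusted arm difference moves by (1 − rho) per unit of baseline imbalance, and that movement accounts for the whole variance loss. A one-standard-error imbalance, sqrt(4/90) = 0.211 SD, shifts it by 0.105, 0.084, 0.063 and 0.042 SD.

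**Step 3: what each coding does.** The arm difference is in delta averaged over sessions 2 to 8, from 600 simulated trials of 90 children per setting. Entries are points of shift per point of baseline imbalance.

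| coding | rho 0.5 | 0.6 | 0.7 | 0.8 |
|---|---|---|---|---|
| no baseline term | 0.487 | 0.401 | 0.292 | 0.219 |
| per-child random slope | 0.479 | 0.393 | 0.282 | 0.215 |
| random intercept per value | 0.323 | 0.315 | 0.237 | 0.192 |
| one overall random coefficient | 0.004 | 0.011 | −0.002 | 0.031 |
| fixed covariate | about 0 | about 0 | about 0 | about 0 |

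The random intercept per value removes from 1 − 0.192/0.219 = 12% to 1 − 0.323/0.487 = 34% of the carry-over, but only 0% to 6% of the SD. It does something because, at SD 12, 90 children share about 40 distinct scores and only about 18% hold a score no other child has.

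The SD of the arm difference falls with a fixed covariate from 1.97 to 1.53, 1.94 to 1.66, 1.58 to 1.40 and 1.32 to 1.20 points. As a check on Step 2, the predicted variance drop is 144 × (4/90) × (1 − rho)² = 1.60, 1.02, 0.58 and 0.26; the simulated drops (1.97² − 1.53², and so on) are 1.54, 1.01, 0.54 and 0.30.

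**Step 4: the named test.** Baseline is common to all four deltas and cancels from any contrast between sessions. In a fitted example the three time x treatment terms (1.0222, −0.1111, −0.8222) and their standard error (1.8929) were identical with and without a fixed baseline main effect.

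**The case against.** The strongest reply is that G3 names the time x treatment interaction as its test, and Step 4 shows that the placement of a baseline main effect does not touch it. That stands. Only a baseline x time term changes that test, and it helps only if the baseline correlation varies over sessions, on which the documents are silent. But delta is already change from baseline, so an arm difference that was the same at all four sessions would give no interaction at all. The larger pre-to-post fall that G3 describes is an arm difference in delta, and that quantity does depend on how baseline is handled.

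A second reply is that listing baseline may be loose wording for ordinary covariate adjustment. That is possible, and one of the three codings would nearly achieve it. The text does not say so.

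A reader might infer three stronger things. One is that G3 gives no baseline adjustment at all; that fits the per-child slope only. Another is that the SCARED comparison is biased; under 1:1 randomisation the unadjusted change-score comparison is valid and unbiased on average. The third is that chance imbalance is a further harm on top of lost precision; Step 2 shows that they are one cost.

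**Conclusion.** The point holds as an undefined coding with a precision cost. Under the G3 wording, the arm difference in SCARED delta may be adjusted for baseline essentially not at all, partly, or almost fully. Where it is not adjusted, the single-visit variance is 1.33 to 1.11 times that of a fixed-covariate analysis for rho of 0.5 to 0.8. The range rests on equal SDs and on a correlation the documents do not supply; at the upper end the loss is modest. The interaction test over sessions 2 to 8 is not harmed by the missing baseline main effect.

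Because C1 and part of G3 make PARS primary, the documents do not support reading this as a defect in the trial's primary analysis; the model may be a secondary one. The change is worth making because the score is already collected and the correction is nearly free.

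**What to change.** Replace the model sentence in G3 with wording such as: *time, treatment, time x treatment, baseline SCARED and baseline SCARED x time are fixed effects; subject is a random effect.* Then state that the pre-to-post hypothesis is tested by the baseline-adjusted arm difference in delta at session 8. Without a named contrast, the rewrite leaves open what is being tested. Say also whether the interaction test is kept as a supporting analysis.

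The cost is two sentences of plan text and a few degrees of freedom: one for baseline plus three for baseline x time if the four sessions are categorical. No new data are needed. The change should be made before SCARED results are compared by arm; if that has already happened, date the change and report both analyses.

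### The time x treatment test that G3 names for delta SCARED does not test the pre-to-post hypothesis it is tied to: it tests only whether the arm difference changes between sessions 2 and 8

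*Combined protocol and SAP*

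**What the plan says.** The first paragraph of G3 defines the outcome: "Total SCARED scores at sessions 2, 4, 6, and 8 will be subtracted from the baseline SCARED score". It then specifies a mixed repeated-measures model in which "delta SCARED scores are the dependent variable". The fixed effects are time, treatment and their interaction, and "baseline SCARED scores and subject within treatment are random effects". The hypothesis is tied to one term of this model, a "significant time x treatment interaction, with a greater decrease in anxiety from pre- to post- training in the active relative to the sham group". G3 names neither the treatment effect nor a session-8 contrast as the SCARED test.

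The same paragraph states: "The primary outcome will be reduction in symptoms of anxiety as measured by the SCARED in study Phase 2". The documents do not define a Phase 2. The second paragraph of G3 states: "The primary outcome will be reduction in symptoms of anxiety as measured by the PARS", in agreement with C1, and gives the PARS a different analysis: "We will perform a 2 x 2 ANOVA with treatment arm (active versus sham) and time (pre- versus post-training) as effects of interest". For missing data, G4 says the trial will "carry the last observation forward".

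Under F4, both child and parent complete the SCARED on the days of sessions 2, 4, 6 and 8. A parent-report SCARED is taken at phone screening (F1) and a child SCARED at Visit 1 (F2). G3 does not say whose score is analysed.

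**The concern.** A time x treatment interaction tests pre-to-post change only if the pre-training value is one of the time levels. In the PARS 2 x 2 ANOVA it is. In the SCARED model the baseline has already been subtracted, so the earliest time level is session 2, after training has begun. G3's words describe a comparison from before to after training, but the term it names compares sessions within training.

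Two things are at stake. A real benefit that is in place by session 2 and lasts would leave nothing for the named test to find. And if the interaction is not significant, a later turn to the treatment effect or to a session-8 contrast would be a choice made after seeing the data, because neither is named.

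**Working it through.** **Structure.** Write B_i for child i's baseline and Y_ik for the score at session k, so delta_ik = B_i - Y_ik. For any two sessions k and l, delta_ik - delta_il = Y_il - Y_ik, and B_i is gone. Let D_k be the active-minus-sham difference in mean delta at session k (positive favours active).

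- Interaction null: D_2 = D_4 = D_6 = D_8.
- Stated hypothesis: D_8 > 0.

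If D_2 = D_4 = D_6 = D_8 = c > 0, the hypothesis is true and the interaction is exactly zero. This needs no assumed SD, correlation or effect size. The baseline random effect does not alter it, because baseline is constant over time within a child. As a numerical check, in one simulated complete data set the interaction F(3, 264) was 2.906 with delta as outcome, with raw scores, with noise in place of baseline, and with 5 SD of benefit added to the active arm at every session.

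**Power.** The plan gives no power for this interaction. The 83% in G1 is for a two-group comparison at an effect size of 0.3 with no metric stated. Read as an SD difference, 0.3 with 45 per arm gives 29%; read as a correlation, it gives 82% to 84%. That is a separate matter, and nothing below rests on the 83%.

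From the documents: 90 children allocated 50/50, so n = 45 per arm; two-tailed testing; sessions 2, 4, 6 and 8. Assumed, not in the documents: SD 1, compound symmetry with correlation rho = 0.5, alpha 0.05, no dropout, and an arm difference at session 8 of 0.6 or 0.3 SD. (A two-group comparison with 45 per arm needs about 0.62 SD for 83% power, so 0.6 is near what the stated power implies; 0.3 is G1's figure read as SD units.)

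Noncentrality, with arm differences d_k and mean m:

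- Interaction, 3 and 264 df: (n/2) Σ(d_k - m)² / (1 - rho)
- Linear trend, 1 and 264 df: (n/2) (-3d_2 - d_4 + d_6 + 3d_8)² / [20(1 - rho)]
- Session-8 change contrast, 1 and 88 df: (n/2) d_8² / [2(1 - rho)]
- Session-8 contrast adjusted for baseline, 1 and 87 df: (n/2) d_8² / (1 - rho²)

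Worked case, linear growth from baseline (0.15, 0.3, 0.45, 0.6): m = 0.375 and Σ(d_k - m)² = 0.1125. The interaction noncentrality is 22.5 × 0.1125 / 0.5 = 5.06, giving 44%. The trend has the same 5.06 on 1 df, giving 61%. Session 8: 22.5 × 0.36 / 1 = 8.1, giving 80%; adjusted, 22.5 × 0.36 / 0.75 = 10.8, giving 90%.

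| Arm difference at sessions 2, 4, 6, 8 (SD) | Σ(d_k - m)² | Interaction, 3 df | Linear trend | Session 8, change | Session 8, adjusted |
|---|---|---|---|---|---|
| 0.6, 0.6, 0.6, 0.6 | 0 | 5% | 5% | 80% | 90% |
| 0.3, 0.6, 0.6, 0.6 | 0.0675 | 27% | 27% | 80% | 90% |
| 0.15, 0.3, 0.45, 0.6 | 0.1125 | 44% | 61% | 80% | 90% |
| 0, 0.2, 0.4, 0.6 | 0.2 | 70% | 85% | 80% | 90% |
| 0.1, 0.1, 0.6, 0.6 | 0.25 | 81% | 85% | 80% | 90% |
| 0, 0, 0.6, 0.6 | 0.36 | 93% | 95% | 80% | 90% |
| 0.3, 0.3, 0.3, 0.3 | 0 | 5% | 5% | 29% | 37% |
| 0.075, 0.15, 0.225, 0.3 | 0.0281 | 13% | 20% | 29% | 37% |
| 0, 0, 0.3, 0.3 | 0.09 | 36% | 43% | 29% | 37% |

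At rho = 0.7, linear growth to 0.6 SD gives 67% (3 df) or 83% (trend), against 95% and 98% for the session-8 contrasts.

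**Treatment main effect.** It averages the four deltas. Its noncentrality is (n/2) m² / [1.25(1 - rho)]. For (0, 0, 0.6, 0.6) at rho = 0.5, m = 0.3, so 22.5 × 0.09 / 0.625 = 3.24, which gives 43% against 80% for session 8. It answers a third question, about average benefit over sessions 2 to 8.

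**The case against.** The strongest reply is that G3 states the intended comparison in words and already has treatment in the model, so the session-8 difference can be estimated with no new data or new model. That is true, and it makes the repair cheap. It does not make the plan right as written: the only term tied to the hypothesis is the interaction.

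A second reply is that training effects may take time to appear, and then the interaction does well. This also stands. With no benefit until after session 4, it beats the session-8 contrast at both effect sizes in the table. A reader might infer that the interaction is always the weaker test, or that it is weaker whenever some benefit is present by session 2. Neither follows: (0.1, 0.1, 0.6, 0.6) gives 81% or 85%, against 80% unadjusted and 90% adjusted. The documents give no trajectory, so no general ranking can be claimed.

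A third reply is that the PARS is primary under C1 and the second paragraph of G3, in a trial that C1 calls a pilot. A reader might infer that the trial's main efficacy test is invalid. The documents do not support that: the PARS ANOVA has pre- versus post-training as its time factor, so its interaction is the right contrast. How much the SCARED flaw matters depends on the unresolved conflict over which scale is primary.

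**Conclusion.** The mismatch between the named SCARED test and the stated hypothesis is certain. It follows from the definition of delta and the list of time points, given complete data, which G4's carry-forward is meant to supply. The pre-to-post hypothesis corresponds to the session-8 arm difference in delta; neither the interaction nor the treatment main effect is that test.

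The size of the loss is not certain. Under the stated assumptions, interaction power for a 0.6 SD benefit at session 8 runs from 5% to 95% depending only on when the benefit appears, while the session-8 contrast stays at 80% (90% adjusted). At 0.3 SD the interaction runs from 5% to 43%, against 29% (37% adjusted). The defect is thus one of target, with a power cost that may be severe, slight or reversed. It should be fixed. It bears on the main result if the SCARED is primary, and on a secondary analysis if the PARS is confirmed.

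**What to change.** In G3, replace the interaction as the named SCARED test with the active-minus-sham difference in delta SCARED at session 8, from the same model, with baseline SCARED as a fixed covariate instead of a random effect. Say whether the child's or the parent's score is used, and use the same informant at baseline and session 8. Keep time x treatment in the model and report it as a description of timing. Reconcile C1 and the two paragraphs of G3 on whether the SCARED or the PARS is primary.

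This takes a few sentences and no new data. There are three costs. Some power is given up if benefit appears only late. The session-8 value depends directly on G4's carried-forward scores. And the planned study period ended in June 2019 while this version is dated 12/10/2020, so if SCARED data have already been seen by arm, the change must be reported as made afterwards.
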